6.2.1. Exposure

There will be two main treatment cohorts for this study:

• Cohort 1: E4/DRSP, a COC containing 14.2 mg of E4 and 3 mg DRSP.

Cohort 2: EE/LNG, containing COCs.

6.2.2. Selection of study population

Approximately 50,500 E4/ DRSP users and 50,500 EE/LNG new users, including adolescents (below the age of 18 years eligible based on local legislation) will be recruited via recruitment centres. Based on experience from previously conducted studies of this type by the investigator team, the proportion of adolescents is expected to range between 4 and 15%, depending on the local prescription behaviour, regulatory framework, and the willingness to participate. Overall, 101,000 study participants are needed to provide approximately 150,000 WY (see Section 6.5), assuming a total drop-out and lost-to-follow-up rate of 15%. More than 60% of study participants will be recruited in Europe and the others will be from the USA and Brazil.

Study participants must meet the following inclusion criteria to be considered eligible for inclusion in this study:

- New users of E4/DRSP

OR

New users of EE/LNG

Supporting document SOP PM01 - Doc PM3004.03

There will be no specific medical inclusion/exclusion criteria, except in Germany where, in accordance with the national recommendations, the protocol describes in section 6.2 how recruitment centres will be instructed to recruit only study participants who are prescribed the COC within on-label use. In summary, recruitment of study participants is conducted via networks of HC-providing HCPs and recruitment centres. Study participants will be considered for enrolment in the study only after the participating HCP has determined that the use of a COC is appropriate. The HCP will explain the nature of the study and facilitate the signing of a study ICF, according to local law. Adolescents (below the age of 18 years) are eligible based on local legislation for study inclusion, provided local regulations regarding co-signature of ICF by a parent or guardian are upheld. All study-related documents are to be approved by the relevant local Ethics Committees and the relevant Data Privacy Office, if applicable.

After enrolment, a study participant may discontinue (and restart) the use of a new COC or may switch to another COC at any time. Participants will be contacted for follow-up until a maximum of two years period is completed, provided they do not withdraw their consent for study participation. Information on the date of study withdrawal during the follow-up phase will be collected.

6.3. Variables

6.3.1. Primary endpoint

The primary endpoint of this study is the incidence rate of VTE, specifically:

- DVT of the lower extremities (ICD-10 codes: I80.1 and I80.2), and
- PE (ICD-10 codes: I26.0 and I26.9)

in E4/DRSP users and users of EE/LNG.

The variable to determine the primary endpoint is:

• The occurrence (or absence) of a new (non-recurrent) confirmed VTE during follow-up.

6.3.2. Secondary endpoints

The secondary endpoints of this study are the incidence rates of:

- All VTEs, including thromboses of the renal, mesenteric, portal, cerebral and retinal veins¹³ (a sensitivity analysis will be done for the ICD-10 code I80.3),
- ATE, including acute myocardial infarction (AMI) (ICD-10 code I21.* ¹³) and cerebrovascular accidents (CVA) (ICD-10 code: I24.9, G45.*, I61.*, I63.1, I63.2, I63.3, I63.4, I63.5, I63.8, I63.9),
- Unintended pregnancy, and
- Neonatal malformations associated with foetal exposure to E4/DRSP and EE/LNG

Estetra PROTOCOL ID 2021_03 V04-00 of 08 September 2022

¹³ ICD-10 codes: I26.0, I26.9, I63.6, I67.6, I80.1, I80.2, I80.3, I80.8, I80.9, I81, I82.0, I82.2, I82.3, I82.8, I82.9, H34.8, K55.0 and N28.0

^{*} For all stars, it means: including all codes within this category

ZEG Berlin

Estetra Study Protocol

Supporting document SOP PM01 - Doc PM3004.03

in E4/DRSP users and users of EE/LNG.

Descriptive measures are applied to compare

- Drug utilization pattern and,
- Baseline risk profile primary and secondary clinical outcomes
 in particular for cardiovascular outcomes

between users of both cohorts.

The variables to determine the secondary endpoints are:

- The occurrence (or absence) of a new (non-recurrent) confirmed VTE during follow-up, including thromboses of the renal, mesenteric, portal, cerebral and retinal veins,
- The occurrence of unintended pregnancy during follow-up.

The variable to determine the drug utilization pattern is:

• The time-varying exposure to COCs observed from study entry through the follow-up period, with dates and duration of each contraceptive prescription.

The variables to characterize the baseline risk profile of COC users are:

- Baseline population characteristics (e.g., age, BMI, family VTE history, and country)
- Socio-economic factors (e.g., education and smoking)
- Parameters of reproductive, contraceptive, and medical history (e.g., gravidity, parity, number of pregnancies/live births, previous use of HCs, disease history [including VTE history] at study entry)
- Concomitant medication.

The variables to determine foetal health outcomes are:

- Occurrence of major congenital malformations, according to classification by the European network of population-based registries for the epidemiological surveillance of congenital anomalies (EUROCAT), as reported during follow-up among pregnancies observed
- Stillbirth (defined as foetal death with a gestational age ≥20 weeks)
- Neonatal death (defined as deaths occurring among live births during the first 28 completed days of life)
- Spontaneous/elective abortion (defined as a loss of pregnancy at a gestational age <20 weeks)
- Termination of pregnancy for foetal anomaly (TOPFA [where prenatal diagnosis was made of malformation in a live foetus and the pregnancy was then terminated])
- Preterm delivery (defined as delivery strictly before 37 completed weeks of gestation)
- Low birth weight (defined as a birth weight <2,500g)
- Small for gestational age infants

The list of variables in Table 1 are similar to the variables used in previous PASS conducted by ZEG-Berlin.

Supporting document SOP PM01 – Doc PM3004.03

Table 1: List of variables to be used in INAS-NEES

		Variable				
X - present; G - present in Germany only; U - present under 18 only; T - present, triggers additional follow up Participant Characteristics		p		Questionnaire		
		Baseline	Follow-up	Extra Follow-up		
	Screening	Did you take an oral contraceptive pill or any other hormonal contraceptive in the last 2 months?	Х			
		Before you were asked whether you want to take part in this study, you and your doctor decided on a new prescription for an oral contraceptive pill. Was the prevention of pregnancy the reason for this prescription?	G			
		Do you have (or have you ever had) a blood clot in a blood vessel of your legs (deep vein thrombosis, DVT), your lungs (pulmonary embolus, PE), or other organs?	G			
		Are you aware of having a disorder affecting your blood clotting – for instance, protein C deficiency, protein S deficiency, antithrombin-III deficiency, factor V Leiden, or antiphospholipid antibodies?	G			
		Do you need an operation or are you off your feet for a long time (e.g., hip/leg surgeries, neurological surgeries, trauma surgeries)?	G			
		Have you ever had a heart attack or a stroke?	G			
		Do you have (or have you ever had) angina pectoris (a condition that causes severe chest pain and may be a first sign of a heart attack) or transient ischaemic attack (TIA – temporary symptoms of stroke)?	G			
Participant Characteristics		Do you have severe diabetes with blood vessel damage?	G			
		Do you have very high blood pressure?	G			
		Do you have a severely increased blood lipids (cholesterol or triglycerides)?	G			
ant (Do you have a condition known as hyperhomocysteinaemia?	G			
rticipa		Do you have (or have you ever had) a type of migraine called 'migraine with aura'?	G			
Pa		Do you have (or have you ever had) a tumour in the liver (benign or malignant)?	G			
		Do you have (or have you ever had) a serious liver disease and your liver function is still not normal?	G			
		Are your kidneys not working well (renal insufficiency)?	G			
		Do you have (or have you ever had) breast cancer or cancer of the genital organs, or is there a suspicion of such a cancer?	G			
		Do you have any unexplained bleeding from the vagina?	G			
		Are you allergic to estetrol or drospirenone, or any of the other ingredients (Lactose monohydrate, Sodium starch glycolate, Maize starch, Povidone K30, Magnesium stearate (E470b), Hypromellose (E464), Hydroxypropylcellulose (E463), Talc (E553b), Cottonseed oil (hydrogenated), Titanium dioxide (E171), Iron (III) oxide red (E172))?	G			
	Demography	Year of birth	Х			
		Height	Х	U		
		Weight	Х	Х		
		Education level	Х			

		Variable		O		
Category		X - present; G - present in Germany only; U - present under 18 only; T - present, triggers additional follow up		Questionnair	re	
Pai	articipant Characteristics		Baseline	Follow-up	Extra Follow-up	
	Gynaec. history	Age at first menstrual period	Х			
		Problems related to period	Х			
		Ever been pregnant before	Х			
		Pregnant in the last 3 months	Х			
		Number of live births	Х			
		Age at first delivery	Х			
	Regular	Taking regular medication	Х	Х	Х	
	Medication	Brand name of regular medication	Х	Х	Х	
Ris	sk Factors		Baseline	Follow-up	Extra Follow-u	
	Family History	Any DVT/PE in close relatives	Х		1 Ollow-u	
	ne como necos de la constitución	Close relatives who experienced DVT/PE	X			
		Any MI/Stroke related death in close relatives	Х			
		Close relatives who died as result of MI/Stroke	Х			
	Diseases	Participant's knowledge of their own risk-factor diseases/conditions	Х			
	Deep Vein	Date of being informed about DVT diagnosis	Х			
	Thrombosis	Was DVT treated by physician?	Х			
		Was DVT treated with blood-thinners?	Х			
	Pulmonary Embolism	Date of being informed about PE diagnosis	Х			
		Was PE treated by physician?	Х			
		Was PE treated with blood-thinners?	Х			
	Myocardial	Date of being informed about MI diagnosis	Х			
1	Infarction	Was MI treated by physician?	Х			
actors		Did ECG/laboratory confirm MI?	Х			
Fact	Stroke	Date of being informed about Stroke diagnosis	Х			
Risk		Was Stroke treated by physician?	Х			
œ.	Thrombophilia	Date of being informed about Thrombophilia diagnosis	Х			
		Was Thrombophilia treated by physician?	Х			
		Type of Thrombophilia	X			
	Cancer	Date of being informed about Cancer diagnosis	Х			
		Type of cancer	Х			
		Was Cancer treated by physician?	Х			
		Was Cancer treated with chemotherapy?	Х			
	Diabetes	Date of being informed about Diabetes diagnosis	Х			
		Was Diabetes treated by physician?	Х			
	High Blood	Date of being informed about HBP diagnosis	Х			
	Pressure	Was HBP treated by physician?	Х			
	Other Severe	Description of Other severe disease	Х			
	Disease	Date of being informed about Other severe disease diagnosis	Х			

		Variable			
Category		X - present; G - present in Germany only; U - present under 18 only; T - present, triggers additional follow up		Questionnair	e
Par	ticipant Character	stics	Baseline	Follow-up	Extra Follow-up
		Was Other severe disease treated by physician?	Х		
Ì	Surgery	Description of surgery	Х		
		Date of surgery	Х		
	COVID-19	COVID-19 infection	Х	Х	
	Liver disease	Liver disease	Х		
	Renal disease	Severe renal disease/kidney disease	Х		THE STATE OF THE S
	Migraine	Migraines with neurological symptoms	Х		
Ì	Tobacco use	Smoking habit	Х	Х	Х
		Years of regular smoking	Х		
		Per day smoking	Х	Х	Х
		Vaping habit	Х	Х	Х
		Years of regular vaping	Х		
		Per day vaping	Х	Х	Х
Но	rmonal Contracept	ive Therapy	Baseline	Follow-up	Extra Follow-up
	Past Therapy	Any hormonal contraceptive use before study	Х		
		Total duration of all hormonal contraceptive use before study	Х		
Ŋ	Change	Change or cessation of hormonal contraceptive therapy since last contact		Х	
erak	Current Therapy	Brand name of current hormonal contraceptive	Х	Х	
Contraceptive Therapy		Indication for current hormonal contraceptive prescription Non-contraceptive indications for current hormonal	X		
cepti		contraceptive prescription Date of current therapy start	_ ^	X	
ıtra	Ctannad Thorany		V		
Co	Stopped Therapy	Brand name of most recently stopped hormonal contraceptive	Х	X	
ona	16.4.4.11.1	Date of therapy stop		X	
Hormonal	If Multiple Therapies	Brand name of previous hormonal contraceptive		X	
Ĭ	Since Last	Date of previous therapy start		X	
	Contact	Date of previous therapy stop		X	
		Treatment gap of min. 1 month when switching to previous therapy		X	
Eve	Duration of treatment gap in months ents of Interest - Diseases		Baseline	Follow-up	Extra
	Diagnoses	Newly diagnosed disease in study objective scope		X	Follow-u
t-	New	since last contact Date of New DVT diagnosis		X	
ere	Deep Vein	Was New DVT treated by physician?		X	
r	Thrombosis Diagnosis	Exact diagnosis for New DVT	-	X	
s of	Diagnosis	Symptoms experienced of New DVT	 	X	
Events of Interest -		Body parts affected by New DVT		X	
Ev		Incidental risk factors experienced up to 6 weeks before New DVT		X	

E 190	Variable			
ategory	X - present; G - present in Germany only; U - present under 18 only; T - present, triggers additional follow up			
articipant Characteri	stics	Baseline	Follow-up	Extra Follow-u
	COVID-19 vaccination in the 6 weeks before the New DVT symptoms		Х	
	Brand name of COVID-19 vaccine		Х	
	Was New DVT treated with blood-thinners?		Х	
	Brand name of blood-thinner		Х	
	New DVT examinations		Х	
	New Genetic Thrombophilia examinations		Х	
	Result of New Genetic Thrombophilia Examination		Х	
	Type of New Genetic Thrombophilia		Х	
New	Date of New PE diagnosis		Х	
Pulmonary Embolism	Was New PE treated by physician?		Х	
Diagnosis	Exact diagnosis for New PE		Х	
40.00	Symptoms experienced of New PE		Х	
	Incidental risk factors experienced up to 6 weeks before New PE		Х	
	COVID-19 vaccination in the 6 weeks before the New PE symptoms Brand name of COVID-19 vaccine		X	
	Was New PE treated with blood-thinners?		X	
	Brand name of blood-thinner		X	
	Hospital admission for New PE		X	
	New PE examinations		X	
	SUMMORNOUS OF AN AND ANADOMORNOUS CONTROLLED TO THE SUMMORN OF THE		X	
	New Genetic Thrombophilia examinations		X	
	Result of New Genetic Thrombophilia Examination		X	
	Type of New Diagnosed Thrombophilia			
	Concurrent DVT diagnosis during New PE		X	
	Date of Concurrent DVT diagnosis		X	
	Body parts affected by Concurrent DVT		X	
New Myocardial Infarct	Date of New MI diagnosis		X	
Diagnosis	Was New MI treated by physician?		X	
	Exact diagnosis for New MI		X	
	Symptoms experienced of New MI		X	
	Did ECG/laboratory confirm New MI?		X	
	Hospital admission for New MI		X	
	Surgical intervention for New MI		Х	
	Type of surgical intervention for New MI		X	
New Stroke Diagnosis	Date of New Stroke diagnosis		Х	
	Was New Stroke treated by physician?		Х	
	Type of New Stroke		X	
	Exact diagnosis for New Stroke		Х	
	Symptoms experienced of New Stroke		Х	
	Duration of New Stroke symptoms		X	

0-1	Variable					
X - present; G - present in Germany only; U - present under 18 only; T - present, triggers additional follow up		Questionnaire				
Participant Characteristics			Follow-up	Extra Follow-up		
	Hospital admission for New Stroke		Х			
	New Stroke examinations		Х			
	Did examination confirm New Stroke?		Х			
	Type of therapeutic intervention for New Stroke		Х			
Events of Interest - Pregnancies and Deliveries			Follow-up	Extra Follow-up		
New Pregnancy	New Pregnancy since last contact		Х			
18	Was New Pregnancy planned?		Х			
	Duration of trying to get pregnant in months, if planned		Х			
	New Pregnancy despite using hormonal contraception		Т			
	Hormonal contraceptive used at time of conception of		Х			
	New Pregnancy Potential reasons for New Pregnancy despite using		V			
	hormonal contraception		X			
	New Pregnancy diagnosis by HCP?		Х			
	New Pregnancy diagnostic method		Х			
	Age of New Pregnancy when diagnosed		Х			
	New Pregnancy status at response date		Х	Х		
es	Due date of New Pregnancy		Х			
Interest - Pregnancies and Deliveries	Reason for New Pregnancy end		Х	Х		
	Malformation/chromosomal abnormality of New Pregnancy		Х			
	Malformation/chromosomal abnormality diagnostic method		X			
	Frequency of alcohol consumption during New Pregnancy		X	X		
	Folic acid taken before New Pregnancy diagnosis		Х	Х		
	Folic acid taken during first 3 months of New Pregnancy		X	X		
	Complications related to the New Pregnancy			Х		
	Infections during New Pregnancy			Х		
New Delivery	New Delivery since last contact		Х			
	Week of Gestation at New Delivery		Х	Х		
	Date of New Delivery		Х	Х		
	Weight of child born during New Delivery		Х	Х		
	Height of child born during New Delivery		Х	Х		
	Malformation/chromosomal abnormality diagnosed in child born		Х	Х		
	Type of Malformation/chromosomal abnormality diagnosed		X	X		
	Malformation/chromosomal abnormality diagnostic method		Х	Х		
	Malformation/chromosomal abnormality family history of biological parents		Х	Х		
	Malformation/chromosomal abnormality diagnosed in biological parents		Х	Х		
	Close family relation between biological father and mother		Х	Х		

Supporting document SOP PM01 - Doc PM3004.03

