The combined oral contraceptive (COC) containing estetrol (E4) and drospirenone (DRSP) (E4/DRSP) is a novel oral contraceptive containing a fixed dose of E4 (14.2 mg) and DRSP (3 mg). E4 is a natural oestrogen only produced during pregnancy by the foetal liver. When combined with the progestin DRSP, ovulation is inhibited. The E4/DRSP combination may have less impact on hepatic and haemostasis parameters in comparison to combinations of ethinyl estradiol (EE) and levonorgestrel (LNG) or EE and DRSP. Yet, it is unknown whether this regimen has an impact on the cardiovascular risk associated with the use of hormonal contraceptives.

Research question and objectives

The primary objective of the study is to characterize and compare the risks of E4/DRSP with EE/LNG, in a study population that is representative of the actual users of these preparations. This includes an estimate of the absolute risk of rare serious adverse outcomes. The main clinical outcome of interest is venous thromboembolism (VTE), i.e., deep venous thrombosis (DVT) of the lower extremities and pulmonary embolism (PE). Secondary objectives include measuring the occurrence of unintended pregnancy, assessing the risk of arterial thromboembolism (ATE), describing the drug utilization pattern, describing the baseline risk profile for VTE and ATE, and investigating outcomes associated with foetal exposure to E4/DRSP.

Study design

Multinational, comparative, prospective, active surveillance study that follows two cohorts. The cohorts consist of new users (starters¹ and restarters²) of two different groups of hormonal

First-ever user of a COC

User who restarts hormonal contraceptive use with a COC (same COC as before or new COC) after an intake break of at least two months.

Supporting document SOP PM01 - Doc PM3004.03

contraceptives: E4/DRSP and EE/LNG. The study is taking a non-interventional³ approach to provide comprehensive information on these treatments in a routine clinical practice setting. Study participants will be enrolled via an international network of COC-prescribing health care professionals (HCPs) and then followed up for one to two years. All outcomes of interest will be captured by direct contact with the study participants. Reported outcomes of interest will be validated via attending physicians and relevant source documents. The classification of outcomes of interest into 'confirmed' and 'not confirmed' will be verified by blinded independent adjudication.

Population

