Based on the above argumentation, it is worth considering a scenario with a less conservative margin choice, i.e., that E4/DRSP has a decreased risk of VTE compared to LNG-COC and the subsequent sample size calculations for the proposed PASS study could be modified accordingly (Table 3).

Table 3: Sample size calculations assuming differing incidence rates between cohorts.

Inc. COC _{LNG}	Inc. E4/DRSP	HR₀	HR_{ni}	Expected #VTE	WY _{Total}	Power (%)
0.0007	0.000561	0.8	1.5	95	150,000	92%

Inc.: incidence of VTE; COC_{LNG}: Levonorgestrel-containing combined oral contraceptive; E4/DRSP: Estetrol/ Drospirenone; HR: Hazard ratio; #VTE: Number of venous thromboembolisms; WY: Women-year

Supporting document SOP PM01 - Doc PM3004.03

For this sample size calculation, the assumption is that the feasibility limit for a prospective non-interventional study of COC is 150,000 WY. Assuming a hazard ratio of 0.8 and an EE/LNG VTE incidence of 7.0 VTE/10,000 WY, the study would have sufficient power to exclude a 1.5-fold risk with 92% power.

The proposed sample size for the investigation of the VTE risk is also sufficient for the evaluation of unintended pregnancy assuming an incidence between 0.5-0.8 per 100 WY (Pearl Index). However, acute myocardial infarction and stroke are very rare in a female population of reproductive age. This study is powered to exclude a 2.5-fold risk of ATE (a secondary outcome). This is sufficient to screen for safety signals.

Table 4 Expected observation time

Assumptions: approx. 101,000 study participants recruited over 60 months (~ 1,684 per month); follow-up of study participants 2 years; drop-out rate of 0.7% per month (e.g., 12 out of 1,684 recruited women will drop-out during the first month after recruitment; therefore, the average number of women during the first month is 1,678 women [(1,684+1,672) x 0.5]); LTFU, end of observation due to treatment stopping or switching, and dropout is expected with approx. 20%.

	Sub-cohorts recruited during the month					
Time after study start	1	2		60		
[month]	Average number of women in follow-up					
1	1,678					
2	1,666	1,678				
		1,666				
24	1,428	•••	***			
25		1,428				
26						
60				1,678		
82				1,438		
83				1,428		
WY	3,099	3,099	3,099	3,099		
Total WY (crude)	185,953					
Total WY (Corrected regarding treatment adherence, treatment stopping/switching, LTFU/dropout)	≈150,000					

ZEG Berlin

Estetra Study Protocol

Supporting document SOP PM01 - Doc PM3004.03

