6.6. Data management

6.6.1. Databases

During the study, two different types of data will be collected: (I) administrative data, which includes contact details of the study participants, and (II) study data, which includes all questionnaire data including baseline data, all subsequent follow-up forms, and all event validation forms. All study data will be collected and managed through the EDC System stored on a cloud infrastructure. This EDC system will be annex 11 and part 11 compliant. For data security and privacy reasons, administrative data are stored separately from the study data. Access to administrative data will be restricted and only be accessible for the teams who require contact with the study participants.

Physician/health care professional details are entered and maintained in the EDC System. Study participants' details are connected to a user account and can only be adapted by the study participants.

Study data will be entered directly by the study participants via an ePRO questionnaire following the Bring Your Own Device (BYOD) concept.

Event data collected during the event validation process will be entered in dynamical additional forms. These forms are restricted to the responsible ZEG Berlin employees or the national field organization.

The quality control of entered data will be supported by edit checks which include range, coding, missing and data checks as well cross-reference (consistency) checks between variables. Any inconsistencies or unanticipated answers will be clarified with the study participant in additional contacts. In case of complex data checks, additional checks may be implemented outside of the EDC system and will be sent via queries to the field organizations for further clarification.

All VTE and ATE outcomes will be coded using ICD-10 and all other reported AEs, as well as pregnancy and surgical procedures will be coded only using the MedDRA dictionary (Medical Dictionary for Regulatory Activities). Collected concomitant medication during baseline, follow-up, or event validation will be coded using the World Health Organization Anatomical Therapeutic Chemical Classification System (WHO ATC)-Codes. Where applicable, ZEG Berlin might also use additional codes for the coding of events (e.g., the outcome of unintended pregnancy: induced or spontaneous abortion, delivery of a healthy child, birth defects).

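### The ICD-10 lists for the two secondary thromboembolic endpoints do not match the endpoints they name: I63.0 is in neither list, I61.* (haemorrhage) is counted as arterial thromboembolism, and N28.0 (renal infarction) is listed under All VTE.

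*Protocol*

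**What the plan says.** The aim for the arterial endpoint, in the protocol abstract, is "assessing the risk of arterial thromboembolism (ATE"). Sections 5.2 and 6.3.2 define it with the same codes: I21.* for myocardial infarction and "cerebrovascular accidents (CVA) (ICD-10 code: I24.9, G45.*, I61.*, I63.1, I63.2, I63.3, I63.4, I63.5, I63.8, I63.9") for the cerebrovascular part. A footnote explains the star as "including all codes within this category", so all of I61 and all of G45 count.

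The All-VTE endpoint is described as including "thromboses of the renal, mesenteric, portal, cerebral and retinal veins". Its codes are in footnotes to the same two sections, again identically: "I26.0, I26.9, I63.6, I67.6, I80.1, I80.2, I80.3, I80.8, I80.9, I81, I82.0, I82.2, I82.3, I82.8, I82.9, H34.8, K55.0 and N28.0".

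Section 6.6.1 makes the classification binding: "All VTE and ATE outcomes will be coded using ICD-10". Section 6.5 attaches an inferential claim to the arterial endpoint: "This study is powered to exclude a 2.5-fold risk of ATE (a secondary outcome"), and calls this enough to screen for safety signals. Neither section explains why I61.* or N28.0 is included or why I63.0 is absent.

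**The concern.** The variables that Section 6.3.2 lists for the secondary endpoints include confirmed VTE and unintended pregnancy but nothing for ATE. The code list is therefore the nearest thing to an operational definition of ATE in that section. If it admits bleeding events and leaves out one type of arterial thrombotic infarct, it does not define the endpoint in its name.

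The claim at stake is the exclusion of a 2.5-fold ATE risk. Events that treatment does not affect move a hazard ratio towards 1. In a study that aims to exclude a risk, that makes a reassuring conclusion easier to reach. Section 6.5 itself calls infarction and stroke very rare in this population, so a few cases assigned differently could matter. For All VTE, the issue is an arterial code in a list described in terms of veins.

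**Working it through.** **1. Compare the two lists over the I63 subcodes** (.0 to .6, .8 and .9):

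| Code | ATE list | All-VTE list |
|---|---|---|
| I63.0 | no | no |
| I63.1 to I63.5 | yes | no |
| I63.6 | no | yes |
| I63.8, I63.9 | yes | no |

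I63.0 is the only one in neither list. This can be seen on the page. The lists are the same in Sections 5.2 and 6.3.2, so it is not a slip in one place.

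**2. Compare codes with endpoint names.** The protocol prints codes without labels; the meanings below come from ICD-10, the classification it prescribes.

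| Code | Meaning | Where listed | Fit |
|---|---|---|---|
| I63.0 | Cerebral infarction, thrombosis of precerebral arteries | Neither | Arterial thrombotic event left out |
| I61.* | Intracerebral haemorrhage | ATE | Not thromboembolic |
| N28.0 | Ischaemia and infarction of kidney (renal artery) | All VTE | Arterial; I82.3 (renal vein) is already listed |
| K55.0 | Acute vascular disorders of intestine | All VTE | Arterial or venous |
| I24.9 | Acute ischaemic heart disease, unspecified | ATE, under CVA | In the composite either way; filing only |

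**3. Does validation correct the lists?** Under Section 6.4.3 and Annex 3.2, adjudicators sort cases into confirmed and not confirmed. Section 6.4.3 accepts cerebral MRI as high-specificity proof of a cerebrovascular accident, and a haemorrhage can meet that standard. Nothing there removes I61 events from ATE or adds I63.0 to the list. For All VTE the position is better: the variable in Section 6.3.2 is a confirmed VTE, so a record showing a renal artery infarct should not qualify.

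**4. Direction of the effect of I61.\*.** Let q be the share of comparator-cohort ATE events that are haemorrhages, and assume a haemorrhage hazard ratio of 1. Then

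HR observed = (1 − q) × HR true + q.

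With HR true = 2.5:

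- q = 10%: 0.9 × 2.5 + 0.1 = 2.35
- q = 20%: 0.8 × 2.5 + 0.2 = 2.20
- q = 30%: 0.7 × 2.5 + 0.3 = 2.05

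The shares are assumptions; the protocol gives none.

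**5. What that could do to the 2.5-fold claim.** Section 6.5 gives no ATE rate, event count, power or alpha, so its statement cannot be reproduced. To choose a convention, I checked the primary calculation with Schoenfeld's formula, one-sided 0.05 and 80% power: 4 × (1.645 + 0.842)² / (ln 1.5)² gives 151 events, as in Table 2. The same formula for a 2.5-fold margin gives 30 events. With 30 events, the chance of wrongly excluding a true 2.5-fold ATE risk is Φ(√(30/4) × ln(2.5 / HR observed) − 1.645):

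| q | HR observed | Chance of wrongly excluding 2.5 |
|---|---|---|
| 0 | 2.50 | 5.0% |
| 10% | 2.35 | 7.0% |
| 20% | 2.20 | 9.8% |
| 30% | 2.05 | 13.5% |

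Neither the 30 events nor q is in the protocol. The table shows direction and scale, not an estimate.

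**The case against.** The strongest defence is that this is a field study with record validation, not a claims study run on codes. Cases are judged from medical documents, and a report is disproven if a different condition is diagnosed. Adjudicators confirm an event as VTE or ATE, and coding may simply follow that decision. For All VTE this largely stands. A reader might infer that the All-VTE rate will be filled with arterial events, but the confirmed-VTE variable limits that harm. N28.0 is then mainly a wrong entry to delete, and the K55.0 wording makes explicit what the variable already implies.

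A second defence is that I61.* may be deliberate: the component is labelled cerebrovascular accidents, Section 6.5 speaks of stroke, and both terms ordinarily cover haemorrhage. That is fair, but the composite would then be more than arterial thromboembolism, and the 2.5-fold statement would need a different name.

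Third, a reader might infer that an I63.0 infarct counts nowhere. That goes too far. ATE is worded as including the listed events, so no text excludes a confirmed I63.0 case. The list is incomplete and leaves its handling unsettled. Nor would losing such cases add to the dilution: an equal loss in both cohorts costs events and precision but does not by itself move the hazard ratio towards 1.

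Fourth, the dilution figures rest on assumed shares and a haemorrhage hazard ratio of exactly 1. That is correct, and they should not be read as findings. The placement of I24.9 changes nothing in the composite and is editorial.

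**Conclusion.** The code lists are wrong as written on three entries. I63.0 is missing from both, I61.* does not belong in an endpoint named arterial thromboembolism, and N28.0 does not belong in a list of vein thromboses that already has I82.3. Because the protocol fixes these lists itself, this is not detail left to a statistical analysis plan. The lists should be corrected.

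Only secondary endpoints are touched. The primary endpoint (I80.1, I80.2, I26.0, I26.9) and its sample size are unaffected. The effect on the ATE hazard ratio cannot be computed from the protocol. If treatment does not affect haemorrhage, the direction is towards 1, which is anti-conservative for excluding a 2.5-fold risk. The absence of I63.0 rests on the text alone; the other two points rest on the ICD-10 meanings of the codes.

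**What to change.** In Sections 5.2 and 6.3.2, including the footnotes:

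- Add I63.0 to the ATE list.
- Take I61.* out of the ATE composite and report it separately as haemorrhagic stroke, using the stroke-type item already in Table 1. If its inclusion is deliberate, rename the endpoint and report ATE without I61.* alongside it.
- Remove N28.0 from All VTE. Moving it to ATE is not proposed, because that would widen ATE beyond the named infarction and cerebrovascular events.
- State that K55.0 counts under All VTE only when mesenteric venous thrombosis is validated.
- Optionally, move I24.9 to the cardiac codes (editorial).

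The cost is the wording of two code lists and the coding instructions, with no new data collection. It is lowest before outcomes are coded and adjudicated. The downside is somewhat fewer ATE events once haemorrhages leave the composite.
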